ASD Interventions: Treatment of individuals with ASD and co-occurring psychiatric disorders often requires psychopharmacologic and psychotherapeutic interventions to address the aberrant behaviors. Psychopharmacologic medications are frequently used to treat a variety of symptoms in this population.⁶² Risperidone and Aripiprazole are the two antipsychotic medications that have empirically-supported evidence⁶³ and are approved by the U.S. Food and Drug Administration for significantly reducing symptoms of irritability in the ASD youth population, although drawbacks include medication side-effects. It has been proposed that THR might be a safe adjunctive intervention to facilitate lowering medication dosages in this population.⁶⁴ In our prior RCT of THR in youth with ASD¹³ we observed reduced ABC-C Irritability scores approximating 50% of the difference in efficacy between low and high dosages of Risperidone.⁶⁵ Cognitive-behavior therapy (CBT) and behavioral interventions are also often employed to target aberrant behaviors in the ASD population. There is growing evidence that CBT can reduce anxiety symptoms in higher functioning ASD youth who have language abilities and higher intelligence levels (IQ>70).^{28,66} An off-shoot of CBT, mindfulness training (e.g., meditation and breathing techniques), has some preliminary beneficial evidence in higher functioning youth with ASD with increasing patient-reported QOL and decreasing repetitive thoughts.⁶⁷ However, there is limited evidence for the application of CBT to target externalizing symptoms of irritability/aggression in ASD youth, particularly in those more severely affected. Behavioral interventions, including Applied Behavior Analysis (ABA), have a large body of empirically-supported evidence for addressing a broad-range of adaptive skill deficits and aberrant behaviors in youth with ASD, including those with intellectual disabilities (ID).^{68,69} A review of 101 studies of specific forms of behavioral interventions targeting externalizing behavior problems (e.g., aggression, self-injury, property destruction) revealed that a majority of study participants were treated in hospital or residential settings due to their severe symptom presentation and treatments resulted in a more than 80% reduction of problem behaviors compared to baseline.²⁴ However, drawbacks of these behavioral interventions are that they tend to require access to highly specialized clinician expertise, substantial time and intensity to see improvements that are not consistently attained or maintained,²⁸ and involve strategies difficult to implement in community settings.²⁴ Moreover, despite evidence for CBT and other behavioral interventions for ASD youth, most studies have not evaluated long-term effects. The extant body of ASD intervention research discussed by Lerner et al., has "...barely begun to explore the common unique processes by which these interventions 'work', the conditions under which they 'work best' and for whom which type of treatment might be optimal".⁷⁰ The significance of the current proposal includes our aims to assess the putative causal mechanisms, durability and dose of THR for the majority psychiatric subpopulation within ASD, for whom our preliminary evidence indicates may be best responders. Our proposal has the potential to provide evidence for THR as an important adjunct to "mainstream" ASD interventions, targeting a wider functioning range of this population.

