Inclusion criteria: (1) Aberrant Behavior Checklist-Community (ABC-C) ^{31,98} Irritability subscale score ≥ 8 ; (2) Leiter-II¹⁰⁶ Nonverbal IQ standard score ≥ 40 ; (3), meeting the Symptom Criterion score (minimum number of symptoms necessary for a DSM-V²⁷ mood, anxiety, or ADHD diagnosis) on the Child & Adolescent Symptom Inventory 5 (CASI-5);¹⁰⁷ and (4) a confirmed diagnosis of ASD by meeting clinical cut-offs on the Social Communication Questionnaire (SCQ)¹⁰⁸ (≥ 11)¹⁰⁹ and Autism Diagnostic Observation Schedule-2 (ADOS-2).¹¹⁰ Only one child with ASD per family will be included in the study to maintain independent observation of participants. Participants will also require a consistent caregiver (i.e., parent or legal guardian) to complete study outcome measures. We will not exclude participants taking medications, as this is a common occurrence for the target population. However, information regarding medications, dosages, and any changes during the study will be collected from caregivers. Medications or substances that could affect cardiovascular or electrodermal activity (e.g., amphetamines, anxiolytics, anticholinergics, beta blockers) or cortisol levels.¹¹¹ (i.e., smoking or regularly use oral, inhaled, or topical steroids), will be flagged and participant's physiological data collected may be excluded or controlled for in the analyses.

Exclusion criteria: Potential participants will be excluded for any of the following reasons: (1) medical or behavioral issues (e.g., animal abuse or phobia to horses) that prevent participation; (2) being a ward of the state; (3) is judged during the riding center screening to have significant riding experience, as the THR manualized curriculum¹⁶ is designed for beginner riders; (4) exceeding weight limits determined by the individual riding center sites' (Colorado and Maine) safety policies (5) vision, hearing, or physical impairments that would prevent participants from being able to be accurately evaluated (e.g. needing to see materials, see others, respond to questions) by study diagnostic measures or (6) unable to engage safely and independently with horses and others at the riding center. Of note, participants will not be allowed to begin baseline assessments until at least six months have passed from the time they last engaged in mounted EAAT, given pilot evidence for the six-month maintenance of THR effects.¹¹²

Study Design and Research Methods

(See Appendix for Calendar of Events/Timetable Document)

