Supplementary analyses: 1.) It is likely that participants will have changed psychoactive medication during the 10- week intervention period and this change is not balanced between two study arms. History of medication change for each participant will then be documented and characterized into few categories, as appropriate. This category of medication change (to be determined) will be introduced into the statistical models for Aims 1 and 2 to adjust for their potential confounding effect for efficacy and mediation analysis. 2.) to examine the effect of intervention sites (Colorado or Maine), we will tabulate the effect size of THR effect by site and introduce site and site by intervention terms into the models mentioned above for efficacy analysis in order to statistically test the site by intervention interaction effect. 3.) We will explore factors that related to the response to THR intervention traditional variable-centered and the state-of-the-art person-centered methods. We will classify each THR subject as responder or non-response (with criteria to be determined) and use logistic regression to identify baseline demography factors and clinical factors (such as psychological diagnosis) that are associated with the response. Moreover, latent profile analysis will be used to group all the participants into few clusters who share similar demography and baseline clinical characteristics. Difference in intervention effect will be examined across these clusters to determine who are more responsive to the intervention. In the later analysis, the outcome will be change score after intervention, the model will consist of cluster, treatment and their interaction. Test of interaction is of primary interest. 4.) In our previous R01 THR study, we observed that the intervention (Barn or THR) reached it.

Summarize Knowledge to be Gained:

Our proposal aims to move the HAI field beyond efficacy trials, specifically regarding THR:

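### The supplementary efficacy models adjust for medication change during treatment as a confounder, which a post-randomisation variable cannot be for the arm comparison

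*Protocol*

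**What the plan says.** The first item under Supplementary analyses expects that participants are likely to have "changed psychoactive medication during the 10- week intervention period and this change is not balanced between two study arms". Each participant's history of change is to be put into a few categories, still to be determined. That category "will be introduced into the statistical models for Aims 1 and 2 to adjust for their potential confounding effect for efficacy and mediation analysis". The protocol does not say whether the category enters as a main effect or also interacts with time.

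The main efficacy models carry no such term. In the Data Analysis Plan, Aim 1 is a linear mixed model with time, arm and their interaction, an unstructured covariance and all randomised participants. Aim 2 uses the same structure with the six-month visit added.

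Two statements under ASD Interventions in the background matter here. The first is "It has been proposed that THR might be a safe adjunctive intervention to facilitate lowering medication dosages in this population". The second describes two antipsychotics as approved "for significantly reducing symptoms of irritability in the ASD youth population". Irritability is the outcome on which the trial is powered. The inclusion criteria allow medication, and "information regarding medications, dosages, and any changes during the study will be collected from caregivers".

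**The concern.** A confounder of the arm comparison must be a common cause of arm and outcome. Arm is set by randomisation, so nothing that happens in weeks 1 to 10 can be a cause of it. If medication change differs between the arms, the difference is either chance or a consequence of assignment. If it is a consequence, conditioning on it takes out any part of the THR effect that runs through medication. It can also open a non-causal path through whatever drives both medication change and outcome.

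What is at stake is interpretation. The adjusted model is described as confounder control, so if it disagrees with the ITT result a reader may prefer the adjusted figure, although the ITT figure is the one protected by randomisation. For Aim 2, a change made during the 10 weeks would also be conditioned on in the six-month comparison.

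**Working it through.** **Inputs from the protocol (Power analysis).** Irritability fell by 6.9 (SEM 1.66, n = 27) with THR and by 2.3 (SEM 1.8, n = 26) with BA.

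- Difference: 6.9 - 2.3 = 4.6 points, written below as -4.6 (negative favours THR).
- SD of change: 1.66 × √27 = 8.63 and 1.8 × √26 = 9.18, pooled 8.90. The simulation uses 9.

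**Assumed, because the protocol gives no figures.** The rate of medication change in each arm, the effect of a change on irritability, and the link between change and prognosis.

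**Step 1: does the way the term enters matter?** Take the two-visit mixed model with a main effect g of medication change M:

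- Baseline mean = a + b·arm + g·M
- End-of-treatment mean = a + c + (b + d)·arm + g·M
- Mean change = c + d·arm

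M cancels from the change, so with complete data the estimate of d, the THR effect, does not move. In 400 simulated trials of 71 per arm, with moderate assumed dependence, d averaged -4.63 with and without M. With 20% missing at end of treatment it averaged -4.49 both ways, and the largest difference in any one trial was 0.13. With M allowed to act on the change (an M-by-time or time-varying term), it became -3.95.

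**Step 2: bias when the term acts on the change.** For least squares,

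adjusted effect = unadjusted effect - γ × (p_THR - p_BA),

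where γ is the fitted coefficient of M and p is the proportion with a change. Two cases can be done by hand, with M lowering irritability by 4 points and otherwise unrelated to outcome:

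- 30% BA, 10% THR: -4.6 - (-4)(-0.2) = -5.4
- 40% BA, 10% THR: -4.6 - (-4)(-0.3) = -5.8

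If p_THR = p_BA, the bias is zero whatever γ is.

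**Step 3: simulation, 1,000,000 subjects per scenario, total effect fixed at -4.6.** The correlation is between the tendency to change medication and a prognostic factor; a positive value means that children doing worse change more often.

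| Change rate BA / THR | Effect of change | Correlation | Unadjusted | Adjusted |
|---|---|---|---|---|
| 30% / 30% | 0 or -4 | 0 to 0.6 | -4.57 to -4.62 | -4.57 to -4.63 |
| 30% / 10% | 0 | 0 | -4.58 | -4.58 |
| 30% / 10% | 0 | 0.3 | -4.60 | -3.94 |
| 30% / 10% | 0 | 0.6 | -4.61 | -3.29 |
| 40% / 10% | 0 | 0.6 | -4.58 | -2.65 |
| 30% / 10% | -4 | 0 | -4.62 | -5.43 |
| 30% / 10% | -4 | 0.6 | -4.61 | -4.09 |
| 40% / 10% | -4 | 0 | -4.59 | -5.81 |
| 20% / 30% | 0 | 0.6 | -4.61 | -5.26 |
| 20% / 30% | -4 | 0 | -4.60 | -4.20 |

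The unadjusted model returns about -4.6 throughout. Over all scenarios run, the bias lay between -1.22 (-5.81 against -4.59) and +1.93 (-2.65 against -4.58). Bias requires both that change differs by arm and that it is related to outcome.

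**The case against.** Four objections deserve weight.

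- **The analysis is supplementary.** This stands. Nothing lets it replace the ITT models, and neither the primary estimate nor the sample size is touched.
- **Read literally, the efficacy term may do nothing.** This also stands. The text names no interaction with time, although the protocol spells out interaction terms for recent hospitalisation and for site. Step 1 shows that a main effect alone is essentially inert. But an inert term controls no confounding either, so the stated rationale fails on both readings.
- **Medication change can truly confound the mediation analysis.** This stands for path b, from mediator to outcome. The protocol recognises that randomisation does not protect that path, and its inclusion criteria list medications that could affect the physiological measures. Dropping the variable there would lose a relevant control.
- **The link from THR to medication is thin.** In part. The background reports it as something that has been proposed, not as a prediction for these 10 weeks. The expected imbalance is stated without direction or cause.

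A reader might infer that the adjusted THR effect is bound to be biased, or bound to be too small. The documents support neither. Shrinkage follows if children doing worse change medication more often and do so mainly in the BA arm. If the change itself helps the BA arm, adjustment enlarges the estimate. That medication change is a response to the child's course is plausible, but the protocol does not say so.

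**Conclusion.** The concern holds for the supplementary efficacy analyses of Aims 1 and 2. Medication change during the intervention cannot confound the randomised comparison, so the stated reason for the adjustment is wrong. Depending on how the term is entered, the adjustment either leaves the THR estimate essentially unchanged or conditions on a possible consequence of treatment.

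In the second case the adjusted estimate ranged from about -2.7 to -5.8 against a true -4.6, which is roughly 42% too small (1.93 / 4.58) to 27% too large (1.22 / 4.59). These limits rest wholly on assumed rates, medication effects and correlations. They illustrate that the bias can go either way and do not predict its size in this trial. The primary ITT result and the power figures are unaffected. For mediation the point is narrower: the variable has a legitimate role on path b, but ordinary regression adjustment is not valid there if THR itself affects medication.

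**What to change.** **Efficacy (Aims 1 and 2).** Remove the in-trial medication-change covariate and the confounding rationale. Replace it with a supplementary model that adjusts for baseline psychoactive medication, including its interaction with time; by Step 1, a main effect alone could not act on the change. Report medication change by arm as a descriptive outcome beside the unadjusted ITT result.

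**Mediation.** Medication change may be kept as a possible mediator-outcome confounder on path b. Label that model as sensitivity only, and give the reason: ordinary regression adjustment fails if THR affects medication.

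**Cost.** Wording and a different covariate. Current treatment is already recorded on the Child and Caregiver Information Form, and medication changes are already collected from caregivers, so no new data are needed and the sample size stays as it is. The downside is that the efficacy analysis no longer tries to separate the THR effect from concurrent medication changes.

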Power analysis: Because significant intervention effect is the prerequisite of mediation analysis, this study is powered primarily on analyses of the primary outcome, ABC-C irritability. For the primary efficacy analysis at T2, effect sizes were estimated for the primary outcome (ABC-C irritability) based on data from our THR RCT¹³ among participants who had psychiatric diagnosis (N=27 for THR and N=26 for BA, data not published). The irritability score decreased by 6.9 (1.66 SEM) in the THR group and 2.3 (1.8 SEM) in the BA group, resulting in a Cohen's d of 0.62 for efficacy. We will enroll 142 participants (71 per arm). To allow for 20% attrition (which is 1% higher than that in our previous trial) at T₂, the sample size for completer or mediation analysis would be 56 per arm. In this case, we will have 97% power at 5% significance to detect significance of THR efficacy for ITT analysis (Aim1) and 90% power for completer analysis. For the mediation analysis, our previous data indicate that the standardized coefficient for the total effect (path c) is 0.34. There are no previous data available for estimating coefficients for paths a and b. We assume that both coefficients are of medium effect size¹³⁷ and the indirect path will explain half the total effect. That is, $a \times b = 0.17$ (e.g., $a=0.4$, $b=0.43$). In this case, a total sample size of 112 provides 90% power at 5% significance to detect a significant indirect effect. This power estimate is based on the Sobel test and was calculated by the R package, power Mediation. **Table 2** shows the power for analyzing secondary and exploratory outcomes at T₂ if the ES is similar to those from data in our previous RCT. (Based

TABLE 2		Power at 5% significance	
Power from ES	ITT (n=81/arm)	Completers (n=56/arm)	
ABC-C Irritability	97	90	
ABC-C Hyperactivity	94	83	
SRS Social Cogn.	92	80	
SRS Social Comm.	>99	>99	
SALT # diff. words used	>99	>99	
SALT # words used	>99	>99	

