Aim 2 determines if THR outcomes are maintained over time. We propose to address the paucity of HAI research examining long-term maintenance of effects. In addition to our six-month follow-up report¹⁸ in a subset of participants in our THR RCT¹³, to our knowledge, only one other study to date has attempted to prospectively examine residual effects of THR in children with ASD, but it had several methodological limitations including teacher-report measures, lack of a control condition, and an unplanned six-week break during the initial treatment phase.⁹⁶ Information on longer term THR effects has important clinical practice implications, including the possibility that THR could be an adjunctive intervention to the current practice of using psychotropic medications to reduce symptoms of aberrant behaviors in ASD youth.⁷⁴

Aim 3 explores dose and sub-population effects of THR and Barn Activity (BA) interventions. This aim addresses important next steps to advance the HAI field of research. A recent systematic review of HAI research with the ASD population discussed the field’s tendency to employ diverse research methods that lack replication and use of non-homogenous ASD samples, which limits the ability to determine who might benefit the most from HAI and under which conditions.⁷¹ Exploratory analyses of our RCT¹³ sample showed stronger positive outcomes in the subgroup of THR participants with co-occurring psychiatric disorders, which provides support to focus on this group who stands to benefit the most from THR. Additionally, the BA no-horse control group in our RCT¹³ showed significant within-group improvements in irritability and hyperactivity behaviors at the conclusion of the intervention, but we were unable to draw conclusions about the effects of that BA group due to the absence of a nonintervention control. Thus, we aim to both explore the effects of BA compared to a waitlist control and explore the dosing effects of a Hybrid group (i.e., 5 weeks BA followed by 5 weeks THR).

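### The responder logistic regression in supplementary analysis 3 uses THR children only, so it cannot tell factors that predict improvement in either arm from factors that predict greater benefit from THR over BA

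*Protocol*

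**What the plan says.** Supplementary analyses, item 3, opens with its purpose: "We will explore factors that related to the response to THR intervention traditional variable-centered and the state-of-the-art person-centered methods". Two methods follow.

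- **Variable-centered:** "We will classify each THR subject as responder or non-response (with criteria to be determined) and use logistic regression to identify baseline demography factors", together with clinical factors. The population is the THR arm and the outcome is responder status. No comparison with BA is described.
- **Person-centered:** "latent profile analysis will be used to group all the participants into few clusters", with change score as the outcome. Here "the model will consist of cluster, treatment and their interaction", and "Test of interaction is of primary interest".

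Two other places bear on whether children improve without riding. The Aim 3 paragraph of Summarize Knowledge to be Gained says that the BA group of the earlier randomized trial "showed significant within-group improvements in irritability and hyperactivity behaviors at the conclusion of the intervention". The Power analysis gives the planning data: "The irritability score decreased by 6.9 (1.66 SEM) in the THR group and 2.3 (1.8 SEM) in the BA group".

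**The concern.** A baseline factor can be associated with improvement in THR children for two reasons. It may be prognostic, so that children with it improve more whichever group they attend. Or it may modify the effect, so that the advantage of THR over BA is larger in children with it. A model fitted in one arm estimates the sum of the two and cannot split them.

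The distinction matters because finding out for whom THR works is a stated aim of the project. The programme also acts on such findings: an exploratory subgroup result from the earlier trial helped to choose this trial's population. A prognostic factor read as a marker of THR benefit could shape the selection of children in the next study.

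**Working it through.** The protocol states no figure for this analysis, so there is none to reproduce. The check asks how often the THR-only model flags a factor that does not modify the THR effect at all.

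**Inputs from the Power analysis**
- Mean improvement in irritability: 6.9 (THR, N=27, SEM 1.66) and 2.3 (BA, N=26, SEM 1.8).
- SD of change = SEM × √N: 1.66 × √27 = 8.63 and 1.8 × √26 = 9.18; pooled, 8.90.
- Sample size: "the sample size for completer or mediation analysis would be 56 per arm"; 71 per arm are enrolled.
- Significance level 0.05 (General consideration of statistical analysis), taken as two-sided.

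**Assumptions, because the protocol gives no figure**
- Responder threshold: 5 or 7 points of improvement.
- Correlation r between the factor and improvement: 0 to 0.5, the same in both arms.

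**Model.** For a standardized factor x and arm g (1 = THR, 0 = BA):

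improvement = 2.3 + 4.6·g + 8.9·(r·x + √(1 − r²)·e), with x and e standard normal.

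There is no x-by-g term, so the THR effect is 4.6 points at every value of x. Each setting was run 2,000 times. The Monte Carlo standard error is about 0.5 percentage points at a rate of 5% and 1.1 points at 40%.

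**Share of runs in which the factor is significant (range over the two thresholds)**

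| r | THR-only logistic, 56 in arm | THR-only logistic, 71 in arm | Two-arm interaction, linear, 56 per arm | Two-arm interaction, logistic, 56 per arm |
|---|---|---|---|---|
| 0 | 4–5% | 4% | 5% | 5% |
| 0.2 | 19–20% | 24–25% | 5–6% | 5% |
| 0.3 | 39–40% | 50% | 5% | 5% |
| 0.4 | 65–67% | 77–78% | 5–6% | 4–5% |
| 0.5 | 87–88% | not available | 5% | 4% |

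The THR-only model is working as a test of association. Its rejections are errors only if they are read as evidence of a THR-specific effect. A larger sample makes that misreading more frequent.

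**Are such correlations plausible?** Baseline irritability is an obvious clinical candidate, although item 3 does not name it. If the baseline and week-10 scores have equal SDs and correlation ρ, the correlation of baseline with improvement is √((1 − ρ)/2). For an assumed ρ of 0.5 this is 0.50, and for 0.8 it is 0.32. It arises in either arm without any effect modification.

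**Price of the two-arm test.** With a standardized factor and equal arms, the standard error of the interaction is √2 times that of one arm's slope. At r = 0 that is about √2 × 8.9/√56 = 1.68 points per SD of the factor. For 80% power the THR effect must change by roughly 2.8 × 1.68 = 4.7 points per SD, about as large as the whole planning effect of 6.9 − 2.3 = 4.6.

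**The case against.** The strongest reply is that item 3 already contains the right analysis. Its second method uses both arms, tests the interaction, and is the step the protocol ties to finding who is more responsive. The clusters are built from the same kinds of variable as the logistic model. This stands, so a reader should not infer that predictors of response are sought in THR children only. It does not rescue the logistic step: a cluster interaction says nothing on whether a particular factor, such as a diagnosis, modifies the effect.

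A reader might also infer that the findings would be reported as predictors of THR benefit. The protocol does not say so. The logistic step claims only association with response, although the purpose stated at the head of the item invites the stronger reading.

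A third tempting inference is that most THR responders would have responded anyway. Under normality with the planning figures, the BA/THR ratio of response rates is 0.38/0.58 = 0.65 at a 5-point threshold, but it runs from about 0.70 at 3 points to 0.44 at 14, and the protocol fixes no threshold. The planning BA change is also not distinguishable from zero: 2.3/1.8 = 1.28, 95% CI about −1.4 to 6.0. The firmer evidence of BA improvement is the earlier trial's result. Finally, BA is an instructor-led 10-week group, so response there shows what happens without riding, not without treatment.

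The choice of a dichotomous outcome and the open responder criterion are not faults in themselves. The criterion can be left to a statistical analysis plan.

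**Conclusion.** The point holds in a narrow form. The variable-centered analysis, as specified, cannot separate prognosis from differential benefit for individual baseline factors, and the cluster analysis beside it does not fill that gap. If a factor is equally prognostic in both arms, with an assumed correlation of 0.2 to 0.5 and 56 children per arm, the THR-only model flags it in about 19% to 88% of runs, against about 5% for a two-arm interaction test. That range rests on the assumed correlations; the two thresholds tried make little difference. The analysis is supplementary and exploratory, and the efficacy, durability and mediation conclusions do not depend on it. It is a minor point, worth correcting because the protocol already uses treatment interactions for clusters, for site, and for recent hospitalization under Exploratory Aim 3.

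**What to change.** Rewrite the variable-centered step so that each candidate factor is fitted in THR and BA participants together, with arm, factor and arm-by-factor terms on the continuous ABC-C change, parallel to the cluster model. Base any statement on for whom THR works on the interaction estimates with confidence intervals. If a THR-only responder model is kept, present it as descriptive and label its results prognostic.

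The cost is a change of wording; the BA data are collected anyway. The drawback is the low power shown above: only very large interactions would reach significance, so the results remain exploratory and the absence of a significant interaction should not be read as a uniform effect.

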General consideration of statistical analysis: Prior to the start of any formal analyses, data for each variable will be examined to identify unusual values that need to be queried, including outliers, patterns of missing values, and non-Gaussian distributions (i.e., have significant skewness and kurtosis). Baseline demographic and clinical characteristics will be summarized using descriptive statistics and grouped by intervention arms. Between-arm difference in demography and baseline variables will be examined using t-test or chi square test respectively for continuous and categorical variables. Any imbalance that could potentially be a confounding factor for the outcome will be adjusted for in statistical models (see below). The primary efficacy analysis will use the “intent-to-treat (ITT)” principle to test our study hypotheses under practical and realistic conditions where not all participants follow or complete the program. All randomized participants will be analyzed in the ITT analyses. Linear Mixed Effect Model (LMM) will serve as the primary method to handle missing values. Other analyses such as completer analysis and analyses with imputed data will be deemed as sensitivity analysis for efficacy examination. However, for mediation analysis, only participants with both the

mediator (intervening) variable and outcome variables available will be included to explore mechanism of the intervention effect. No interim analysis will be conducted. In all analyses, a $p \leq 0.05$ will be considered significant. SAS and Mplus software will be used for these analyses.

AIM1: Efficacy assessment (for H1a-1c): LMM with unstructured covariance will be used to model baseline and end of treatment (EoT or T_2) primary and secondary outcome measures as well as expanded outcomes where fixed effects include evaluation time (baseline or EoT) and intervention arm indicator (THR/BA), as well as their interaction.

[figure not shown]
Estimate of the interaction will be used to quantify effect size and tested for statistical significance.

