on 18 THR and 11 BA, participants with concomitant psychiatric diagnosis and six-months follow-up ABC-C data from our RCT, the ES for THR effect on the six-month irritability score was 0.45 (not published) as compared to BA participants. In this case, we will have 81% power for the primary ITT analysis (n=81 per arm) to detect the THR effect on ABC-C, but 56% power to see statistical significance for completer analysis. This analysis assumes that 45 participants per arm will be followed six-months after the intervention. Aim 3 is more hypothesis generating and exploratory. 20 extra participants will be enrolled in the wait list group who subsequently received Hybrid intervention. To minimize the imbalance between groups, we will randomize with 1:1:1 ratio the first 60 Colorado participants into BA/THR/wait list group. The minimum detectable effect size needs to be 0.9 (0.74) Cohen's D to have 80% power if 20 wait list (or Hybrid) participants

will be compared to 20 (or 56) other participants.

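### The search for predictors of THR response uses a responder split and logistic regression, which discards information that a linear model of change would keep

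*Protocol*

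**What the plan says.** Item 3 of the Supplementary analyses (Protocol, Data Analysis Plan) plans two looks at who responds to THR.

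- **Variable-centered, THR arm only:** "We will classify each THR subject as responder or non-response (with criteria to be determined) and use logistic regression to identify baseline demography factors". Clinical factors such as diagnosis are included as well.
- **Person-centered, all participants:** latent profile clusters are formed, and then "In the later analysis, the outcome will be change score after intervention, the model will consist of cluster, treatment and their interaction".

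Elsewhere the outcomes stay on their full scale. The efficacy analyses for Aims 1 and 2 are linear mixed models of the scores, and the mediation analysis takes change from T0 to T2 as its outcome. Item 3 gives no reason for treating the variable-centered search differently.

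**The concern.** A yes/no response treats two children just either side of the cut as opposites, and treats a child who barely passes it the same as one who improves greatly. Differences within each class no longer count. With a numeric outcome in hand, that usually lowers the chance of finding a real predictor.

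The protocol commits both to classifying participants and to logistic regression. A later document could settle where the cut falls, but no choice of cut recovers the discarded information.

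At stake is one of several analyses bearing on which youth do best with THR, a question that the protocol's summary of knowledge to be gained puts among its main ones. The THR arm is small for a predictor search, so lost power is not easily spared.

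**Working it through.** **Inputs from the protocol (Power analysis).** Enrolment is stated as "We will enroll 142 participants (71 per arm"). For completers, "the sample size for completer or mediation analysis would be 56 per arm". Table 2 and the six-month calculation use 81 per arm for ITT instead of 71, so 56, 71 and 81 are all tried. The significance level is 0.05, taken as two-sided. The effect size for THR against BA is given as "resulting in a Cohen's d of 0.62 for efficacy".

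**Assumed, because the protocol gives no value.** Predictor strength, responder share, a normally distributed change score, and a single cut of that score. Using 0.62 SD as the effect of a baseline factor only borrows a plausible size; in the protocol it is the between-arm effect.

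**Step 1: reproduce the plan's own power.** No power is stated for the responder analysis. The nearest figure is "we will have 97% power at 5% significance to detect significance of THR efficacy for ITT analysis (Aim1) and 90% power for completer analysis". With power = Φ(d√(n/2) − 1.96):

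- n = 56: 0.62 × √28 = 3.281; Φ(1.321) = 90.7% (90.2% with the t distribution), against 90% stated.
- n = 81: 0.62 × √40.5 = 3.946; Φ(1.986) = 97.6% (97.5% with t), against 97% stated.

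Both agree, which supports the two-sided reading.

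**Step 2: one worked case by formula.** THR arm, N = 56, baseline factor splitting it 28/28, difference 0.62 SD.

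- *Full scale:* Φ(0.62 × √(28/2) − 1.96) = Φ(2.320 − 1.96) = 64.1%.
- *50% responders:* cut midway between the groups, so the response rates are Φ(0.31) = 0.622 and 0.378, difference 0.243. Null SE = √(2 × 0.5 × 0.5/28) = 0.1336; alternative SE = √(2 × 0.622 × 0.378/28) = 0.1296. Power = Φ((0.243 − 1.96 × 0.1336)/0.1296) = 44.3%. Loss: 19.7 points before rounding.
- *30% responders:* rates 0.405 and 0.195, difference 0.210. Null SE = √(2 × 0.3 × 0.7/28) = 0.1225; alternative SE = √((0.405 × 0.595 + 0.195 × 0.805)/28) = 0.1192. Power = 40.1%. Loss: 23.9 points.

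**Step 3: simulate the two regressions.** One predictor, linear regression of change against logistic regression (likelihood-ratio test) of the same change after cutting. Power in %:

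| Setting | Linear | Logistic at 50 / 33 / 25% responders | Loss (points) |
|---|---|---|---|
| r = 0.3, n = 56 | 63 | 46 / 45 / 40 | 17–23 |
| r = 0.3, n = 71 | 73 | 55 / 52 / 47 | 18–26 |
| r = 0.4, n = 56 | 87 | 71 / 68 / 62 | 16–25 |
| r = 0.4, n = 71 | 94 | 80 / 78 / 74 | 14–20 |
| r = 0.4, n = 81 | | | 11–18 |
| binary 0.62 SD, n = 56 | 62 | 43 / 42 / 40 | 19–22 |
| binary 0.62 SD, n = 71 | 72 | 55 / 51 / 47 | 17–25 |

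Over these moderate settings the loss is about 11 to 26 points. The formula in Step 2 runs slightly higher for the binary factor at 25% responders (26.5, 28.4 and 28.6 points at N = 56, 71 and 81). The simulation fits the planned type of model, so it is the better guide.

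**Step 4: outside those settings.**

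- Weak predictors, n = 56: 4 to 6 points at r = 0.15 (linear power itself only 19%) and 9 to 12 at r = 0.2.
- Larger arm, in case the protocol's ceiling of 250 youth were randomized equally to THR and BA (n = 125): 3 to 7 points at r = 0.4, where power nears its limit; at r = 0.3, 93% against 78 / 74 / 72%, a loss of 15 to 21.

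For scale: at r = 0.3, 100 participants split at the median give 69% power, no better than 73% from 71 participants analysed unsplit.

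**The case against.** **The protocol does not say in words that the split is made on the change score.** This stands. Item 3 names no outcome, scale or cut, and a response criterion could combine irritability and hyperactivity, both primary under Specific Aim 1. The calculations model one cut of one normal variable. Splitting the change is still the natural reading, since the outcomes are scores or counts.

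**The loss depends on the inputs.** This also stands. A reader might infer a fixed loss from the moderate settings. The documents do not support that, because predictor strength and responder share are nowhere given. The loss is small where a predictor is too weak for either method, or so strong in a large arm that both succeed.

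**The open threshold.** A reader might infer that the cut will be chosen after several are tried, inflating false positives. The protocol describes no such search, and the definition may be fixed in a statistical analysis plan that is not shown. The unset criterion is therefore not part of this point.

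**Little rests on this regression.** Largely right. The cluster analysis in the same item uses all participants and the full scale, with its interaction test as the main interest. Exploratory Aim 3 adds a recent-hospitalization interaction on the continuous outcome. A reader might infer that the question of who benefits is compromised; the documents do not support that. Nor would a linear model in THR participants alone answer it, because without BA it finds predictors of change, not of benefit over BA.

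**Conclusion.** The point holds as a minor, conditional one. The protocol commits one exploratory analysis to a responder split with logistic regression, gives no reason, and departs from the scale it uses elsewhere. The full-scale analysis had more power in every setting tried.

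The size rests on a normal change score, a single cut and one predictor at a time: roughly 11 to 26 points for moderate predictors, 25% to 50% responders and 56 to 81 THR participants, with smaller losses for the weak-predictor and large-arm cases shown. No primary or secondary conclusion of the trial is affected.

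**What to change.** In Supplementary analyses item 3, replace the responder logistic regression with a linear model of the continuous baseline-to-T2 change in ABC-C irritability, or of the T2 score adjusted for baseline, on the same baseline demographic and clinical factors. Fit the same model to the other outcomes if wanted. Report any responder proportion descriptively only.

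The cost is one sentence of plan wording, with no new data, visits or participants. The small downside is that results come as points of change per factor instead of odds of response; the descriptive proportion partly makes up for that. The text should also say that the analysis, being confined to the THR arm, identifies predictors of change and not of benefit over BA.
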